2. Are speech-evoked brain responses sensitive to distortions in speech and can hearing aid amplification resolve issues with brain responses to distorted speech?
3. Which (statistical) tests are optimal for detection of objective brain responses to speech?
4. Are realistic speech stimuli (words or running speech) able to robustly detect brain responses compared to current clinical standards (clicks and tones)?

Method

In this exploratory study focussing on the feasibility of obtaining objective measurements of responses to speech under aided and unaided conditions, the research questions will be addressed through a series of experiments in a group of up to 40 participants (in total) with mild to moderate hearing loss in the better hearing ear. Participants will undergo a maximum of two test procedures in which they are exposed to speech or speech-like stimuli (clicks, tones, short phonemes, words, repeated sentences and/or continuous running speech such as extracts from audiobooks). Testing will be performed in a sound treated room.

Materials

Recording of the brain responses will be performed using a 32-channel EEG system (ActiveTwo, BioSemi BV, Amsterdam, Netherlands). System components will be applied as per the manufacturer's recommendations to ensure subject safety and optimal brain response recording. The system has obtained EU health and safety approval to be used for conducting research with human subjects. The experimenters will receive prior training from a member of academic staff experienced with the equipment and closely related protocols. The EEG system uses active electrodes, which means scraping of the scalp is unnecessary. This reduces the discomfort for the participants.

Participants

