3. Segments of auditory recording from free audiobooks (found on <https://librivox.org/> or taken from previous studies at the ISVR and the Institute of Hearing Research) will be used. Audiobook segments have been used in various published research related to speech perception and speech intelligibility analysis (Ding and Simon, 2013).

Stimuli will be presented as clear stimuli or degraded by adding noise at different signal-to-noise ratios (SNRs), or by applying signal processing methods that emulate hearing impairment or speech processing in hearing aids.

Stimulus presentation

Stimuli will be presented at maximally 80 dB (A) through loudspeakers. According to the ISVR Task report on noise and vibration ethics (ISVR Technical Memorandum No. 808, 1996), sound levels must be less than 76 dB (A) for an 8 hour exposure during a 24 hour period, to be considered 'usual'. Participants will undergo sessions where the listening time will be maximally 2 hours at a maximum intensity of 80 dB (A). Stimuli can therefore be considered as usual.

Stimulus levels will be controlled using the calibration procedural approach as per ISO 389-8:2004. These settings of the calibration signal directly control the level of the test stimuli. Calibration will be performed at the beginning of the experimental period and every 4 weeks thereafter.

Test procedure

For this study, participants will be asked to participate in two tests. One of the tests will focus on detecting responses to short stimuli (clicks, phonemes and words). A second test will focus on detecting responses to more complex stimuli (tones, sentences and running speech). Tests will be randomised, and be performed with an interval of at least 24 hours between tests.

Test 1: Short stimuli

After participants are sat in the chair and the EEG electrode are fitted, participants will be asked to listen to click stimuli played from a loudspeaker placed 1 meter directly in front of them. Participants will not wear their hearing aid (unaided condition) for this part of the procedure. This part of the study will take about 10 minutes. Clicks would be considered the gold standard for robustness of response detection and used to answer question 4 of the research questions.

After collecting the click stimuli, participants will be asked to listen to repeated word stimuli under aided and unaided conditions. Word stimuli have been used in previous

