experiments with normal hearing participants and showed good detection rate of brain responses. Words will be played as normal and distorted words. Distortions will include high-pass filtered (frequencies above 1000 Hz only) and low-pass filtered (frequencies below 1000 Hz only) versions of the words and words mixed with noise at different signal-to-noise ratios. Each participant will be exposed to 6 conditions listed below, each lasting 7 minutes, in aided and unaided conditions. This means that the total test time will be 12 conditions of 7 minutes, or 84 minutes. Conditions will be randomised during the study. Breaks will be offered between the tests, but researchers will make participants aware they can ask for a break at any time during the procedure. Participants will also be allowed to sleep during this part of the study.

To summarise: the different word conditions are

1. Clean words in quiet
2. Clean words in noise (SNR = 0dB)
3. Clean words in noise (SNR = 3dB)
4. Low-pass filtered words in quiet (0-1000 Hz)
5. High-pass filtered words in quiet (>1000 Hz)
6. High-pass filtered words in quiet (>2000 Hz)

These will be repeated in aided and unaided conditions. This would help in answering questions 1 and 2 of the research questions.

Test 2: Complex stimuli

For this part of the study, participants will be asked to listen to tones and running speech presented from a loudspeaker at 1 meter distance directly in front of them. Running speech will be a segment of about 20 minutes. Participants will be asked to remain attentive during this tests, as we will be measuring cortical responses to speech. To ensure this, they will be asked to answer multiple choice questions regarding the content of the speech presented at random intervals. Participants will perform the experiment twice under aided and unaided conditions. Therefore, a total of 80 minutes of EEG signal to running speech will be collected per participant. Results would be used to answer question 1 and 2 of the research questions.

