Lastly, modulated tones will be presented at frequencies of 1000 Hz under aided and unaided conditions at intensities of 40, 60 and 80 dB (A). Tones will be modulated with a modulation frequency of 40 Hz for 6 minutes. Total test time over the entire test 2 procedure will therefore be 92 minutes. For each of the tones, we will ask the participant to rate its loudness on a seven-point scale ranging from very soft to very loud (Castro, *et al.* 2008). This could be used to help answering question 4 of the research questions.

End of experiment

By the end of the recording session all of the equipment, electrodes, insets and cap will be removed gently from the participant by the researcher. Equipment will be cleaned following the manufacturer's recommendations. At the end of the procedures, the experimenter will give information to the participant about the possibility to become part of a database collecting contact information for participants for future studies at the Royal Berkshire NHS Foundation Trust or University of Southampton.

Data analysis

Data analysis will be performed off-line. Pre-processing and artefact rejection will be performed according to current standards in the research field. Data from tests consisting of repeated stimulus sweeps will be averaged over all sweeps to allow analysis of brain responses. For all tests, the relationship of the response to the

speech stimulus will be performed by comparing the stimulus envelope with spectro-temporal features in the (averaged) brain response. Further analysis will include assessment of coherence and delay measurements between EEG channels during brain responses, as well as temporal and spectral assessment tools and source separation techniques.

Statistical analysis

Power calculation

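### Clicks are always recorded first in Test 1 and tones apparently last in Test 2, so each within-session question 4 contrast is confounded with time in session, and the plan neither randomises nor adjusts for this

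*Combined protocol and SAP*

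**What the plan says.** Question 4 (Research questions) asks whether words or running speech detect brain responses robustly when set against clicks and tones.

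**Test 1 (Test 1: Short stimuli).** Clicks come straight after electrode fitting: "After participants are sat in the chair and the EEG electrode are fitted, participants will be asked to listen to click stimuli". They are unaided and short: "This part of the study will take about 10 minutes". Their role is explicit: "Clicks would be considered the gold standard for robustness of response detection and used to answer question 4 of the research questions". Words follow: "After collecting the click stimuli, participants will be asked to listen to repeated word stimuli under aided and unaided conditions". There are 12 word blocks of 7 minutes (six conditions, aided and unaided), for which the protocol says "Conditions will be randomised during the study". In context this covers the word conditions; clicks are not on that list.

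**Test 2 (Test 2: Complex stimuli).** Running speech of about 20 minutes is heard twice aided and twice unaided, 80 minutes in all. Then: "Lastly, modulated tones will be presented at frequencies of 1000 Hz under aided and unaided conditions". The stated session total is 92 minutes. The protocol says this part could help to answer question 4.

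**Randomisation and analysis.** The order of the two tests is also randomised (Test procedure). Statistical analysis of data names normality checks, correlation, an F-ratio test, analysis of variance and bootstrap methods. It has no term for order, block position or time in session.

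**The concern.** A comparison of stimulus types is clean with respect to time only if the types share the same positions in the session on average, or if position is modelled. Here the word blocks are spread at random over their part of Test 1, but the benchmark they are judged against is held at the start. In Test 2 the benchmark appears to be held at the end. Anything that changes over about an hour and a half of recording, such as electrode contact, arousal or fatigue, then enters the contrast as if it were an effect of the stimulus.

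The protocol itself gives reason to expect some change of state. It allows sleep in the word part of Test 1, offers breaks, and uses content questions to hold attention in Test 2. At stake is the answer to one of the four research questions: speech could look better or worse than a clinical standard partly because of when each was recorded. Because the two benchmarks sit on opposite sides of the speech material, a steady drift would push the two contrasts in opposite directions.

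**Working it through.** **1. Reproduce the stated durations.**
- Words: 12 × 7 = 84 minutes, as stated. With clicks: 10 + 84 = 94 minutes, before breaks.
- Test 2: 20 × 2 × 2 = 80 minutes of running speech. The stated total of 92 needs 12 minutes of tones, that is 6 minutes per aiding condition covering all three levels (80 + 2 × 6 = 92). Reading 6 minutes as the time per tone would give 80 + 6 × 6 = 116.

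**2. Block midpoints.**

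| Session | Reference block | Speech blocks | Gap |
|---|---|---|---|
| Test 1 (94 min) | Clicks 0–10, midpoint 5 | Words 10–94, midpoint 52 | Words 47 min later |
| Test 2 (92 min) | Tones 80–92, midpoint 86 | Running speech 0–80, midpoint 40 | Tones 46 min later |

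On the 116-minute reading the tones occupy minutes 80–116 (midpoint 98) and the gap is 58 minutes. Randomising which test comes first leaves these within-session gaps unchanged.

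**3. What the gap could be worth (assumed drift).** Let background noise at minute t of a session of length T be 1 + r·t/T. For a later block compared with an earlier one, the noise ratio is k = (1 + r·t₂/T) / (1 + r·t₁/T). With averaging, the equivalent loss of recording time is 1 − 1/k². The assumed values are r = 0.10 and r = 0.30.
- Words relative to clicks: r = 0.10 gives k = 1.0553/1.0053 = 1.050, loss 9%. r = 0.30 gives k = 1.1660/1.0160 = 1.148, loss 24%.
- Tones relative to running speech: r = 0.10 gives k = 1.0935/1.0435 = 1.048, loss 9%. r = 0.30 gives k = 1.2804/1.1304 = 1.133, loss 22%.

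If noise fell over the session, the signs would reverse.

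**4. Effect on a test (assumed drift).** Assume no true click–word difference, 40 participants, a paired test at alpha 0.01 (N and alpha borrowed from Power calculation), and a linear drift of D standard deviations of the paired difference over 94 minutes. With clicks fixed first, the bias is D × 47/94 = D/2. Simulation with 4,000 runs per case gave:

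| Assumed D | Bias, clicks first (SD) | False positives, clicks first | False positives, random click slot |
|---|---|---|---|
| 0 | 0 | 1.0% | 0.8% |
| 0.25 | 0.12 | 3.8% | 0.8% |
| 0.5 | 0.25 | 14% | 1.0% |
| 1.0 | 0.50 | 67% | 1.1% |

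**5. Effect of the proposed order.** With 13 equally likely click slots, the mean click midpoint is 6 × 7 + 5 = 47. The mean word midpoint is (94²/2 − 10 × 47)/84 = 47, so the expected gap is 0. With tones first in half of participants, their midpoint there is 6 and that of running speech is 12 + 40 = 52. The gaps of −46 and +46 average to 0.

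**The case against.** **The design is not beyond rescue by analysis.** A reader might infer that stimulus type and time are wholly inseparable and that no analysis could help. The documents do not support that. Word blocks are randomised over minutes 10–94, so a time trend can be estimated from them and carried back to the click slot, if clicks and words share the trend. Roughly position-matched contrasts also exist: clicks against the first word block (minutes 10–17) or the first running-speech segment (0–20), and tones against the last word blocks. Those that cross sessions are helped by the randomised test order. This stands, but none of these analyses is planned, and the trend approach rests on an assumption that randomising the slot would not need.

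**Direction and size are unknown.** It is tempting to say that clicks are favoured and tones disadvantaged. That follows only if recording quality worsens with time, and the protocol gives neither sign nor size. Its permission to sleep in the word part shows that drowsiness was not thought disqualifying there. It is equally tempting to compare the first position with the last, which under the same assumed drift gives 1 − 1/1.1² = 17% to 1 − 1/1.3² = 41%. No within-session question 4 contrast pairs those positions. The only such pair is clicks with tones, two benchmarks in different sessions.

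**The tone wording is weaker.** The opening word of the tone paragraph could mark order of description, and two earlier lists of Test 2 stimuli name tones first. The wording for clicks leaves no such doubt. Still, nothing in the text counterbalances the tones.

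**Mitigation and purpose.** Breaks, artefact electrodes and artefact rejection reduce some causes of drift but do not balance position. The study is exploratory, and recording the reference at one consistent point can be defended. The stimuli also differ in duration, aiding and required state, so balancing order will not make the comparison clean. All this limits the weight of the point. It is not a reason to leave in a bias that is cheap to remove, in a protocol that already randomises the word conditions.

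**Conclusion.** The point holds as a design weakness in the question 4 comparison, not as a demonstrated bias. For clicks the wording is clear: every participant hears them before any word block, with midpoints 47 minutes apart. For tones the same holds in the opposite order, 46 minutes apart on the stated 92-minute total, provided the paragraph describes presentation order. The plan neither randomises the reference blocks nor adjusts for position.

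Under an assumed linear noise rise of 10% to 30% over a session, the gap is worth about 9% to 24% of recording time for words relative to clicks, and 9% to 22% for tones relative to running speech. The drift, its linearity and its direction are assumptions, and breaks are ignored. The false-positive rates rest on assumed drift in the same way and illustrate the mechanism only. The tones come last within Test 2 at most, not last in the study, because test order is randomised.

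**What to change.** - **Test 1:** place the click block at a random position among the Test 1 blocks, still unaided as planned.
- **Test 2:** state the intended order of tones and running speech, and counterbalance it, with tones before running speech in half of participants and after it in the other half.
- **Analysis:** include block position as a term in the question 4 analysis. If the order cannot be changed, specify this adjustment with its common-trend assumption and report the fixed order as a limitation.
- **Reporting:** state that the stimuli also differ in duration, in aiding (clicks are unaided only) and in state (sleep allowed in the word part, attention required in Test 2), and that balancing order does not remove these differences.

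The cost is a longer randomisation list and one model term, with no added recording time. The small downside is that some participants hear the tones before the attentive speech task.

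### Is the 92-minute total for Test 2 wrong, given that tones are presented at three intensities?

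*Combined protocol and SAP*

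**What the plan says.** The Test 2 section describes two kinds of recording.

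- **Running speech.** "Running speech will be a segment of about 20 minutes", and "Participants will perform the experiment twice under aided and unaided conditions". From this the protocol concludes that "a total of 80 minutes of EEG signal to running speech will be collected per participant".
- **Modulated tones.** A 1000 Hz tone is presented with and without the hearing aid at 40, 60 and 80 dB(A). On duration the text says only: "Tones will be modulated with a modulation frequency of 40 Hz for 6 minutes". Participants rate the loudness of each tone.

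The sentence after the tone duration gives the sum: "Total test time over the entire test 2 procedure will therefore be 92 minutes". Separately, the section on stimulus presentation sets a ceiling: "Participants will undergo sessions where the listening time will be maximally 2 hours".

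**The concern.** Three intensities in two aid states make six tone recordings, and a reader coming from Test 1 will expect time to be counted per recording. There, six word conditions of 7 minutes in two aid states are multiplied out to 84 minutes. The same convention in Test 2 gives 36 minutes of tones and a total of 116, so the printed 92 looks as though the three intensities were forgotten. The separate loudness rating for each tone adds to the impression that each is its own 6-minute run.

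Either reading seems to carry a cost. At 6 minutes per recording the stated test time is too short, and little room is left under the 2-hour ceiling. At 2 minutes per recording the tones, which research question 4 names beside clicks as a current clinical standard, rest on much less data than the 7-minute word conditions or the 20-minute speech segments.

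**Working it through.** **Inputs** (all from the Test 2 section except the last)

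- Speech segment: about 20 minutes, 2 repeats, 2 aid states
- Tones: 1 carrier frequency, 3 intensities, 2 aid states
- Tone duration: 6 minutes, unit not stated
- Stated total: 92 minutes
- Listening maximum (stimulus presentation section): 2 hours = 120 minutes

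**Step 1: the speech component.** 20 × 2 × 2 = 80 minutes, which agrees with the stated 80.

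**Step 2: what the stated total leaves for tones.** 92 − 80 = 12 minutes. Over 3 × 2 = 6 recordings that is 12 / 6 = 2 minutes each, if split equally.

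**Step 3: which meaning of the 6 minutes gives 92.**

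| The 6 minutes covers | Tone time (min) | Test 2 total (min) | Equals 92? | Left under 120 (min) |
|---|---|---|---|---|
| all tones together | 6 | 80 + 6 = 86 | no | 34 |
| the three intensities in one aid state | 6 × 2 = 12 | 80 + 12 = 92 | yes | 28 |
| one intensity, both aid states together | 6 × 3 = 18 | 80 + 18 = 98 | no | 22 |
| one intensity in one aid state | 6 × 3 × 2 = 36 | 80 + 36 = 116 | no | 4 |

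Only one of the four readings reproduces the printed figure, and it does so exactly.

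**Step 4: size of the gap on the alternative reading.** 116 − 92 = 24 minutes, and 24 / 92 = 26%. The total is still below 120.

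**Step 5: what depends on the figure.** The power calculation uses a 35 nV amplitude difference, a 30 nV standard deviation, 80% power and alpha 0.01. Tone duration enters none of these, and the statistical analysis section does not use it either.

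**The case for a change.** The strongest case for a change is that 2-minute and 6-minute tone recordings are both defensible from the wording, that the length has to be settled before data are collected, and that a short tone recording cannot be lengthened afterwards. If residual noise falls with the square root of recording time, a 2-minute recording has √(6/2) = 1.73 times the noise of a 6-minute one, which could make tones look less detectable than speech. On the longer reading only 4 minutes remain under the ceiling. The overview of the test procedure also names sentences as Test 2 stimuli, although no time is allotted to them.

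Part of this stands: the time per intensity is not written down. The rest carries less weight.

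- The total directly follows the tone duration and is presented as derived from it, so it shows how the 6 minutes was counted. Where a duration applies to every condition, as for the words in Test 1, the protocol says so; the tone sentence does not. The loudness rating shows that the tones are separate items but says nothing about their length.
- The factor of 1.73 assumes an equal split and stationary noise, and the documents give neither. Duration alone also does not decide which stimulus is easier to detect, because response size and type differ between 40 Hz modulated tones, words and running speech, and no figures are given for the tones.
- The protocol promises no common recording length. Clicks take about 10 minutes, words 7 and speech about 20, by design, in a study that calls itself exploratory. Clicks are named as the reference standard for detection; the tone part is offered only as something that could help with question 4.
- The 4-minute margin arises only on the reading that the stated total excludes. On the reading that matches it, 28 minutes remain. The behavioural speech-in-noise test is not tied to the Test 2 day, so it cannot be counted against either margin.

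**Conclusion.** The concern does not call for a change. The sums behind it are correct, but 116 minutes appears only if a per-tone qualifier is added to a sentence that lacks one. Read as 6 minutes per aid state, the plan agrees with its own total of 92. What remains is an unstated recording time per intensity, which staff who set up the tone block can infer from that total, and analysts will in any case see the length of each recording in the data. At most the discrepancy is 24 minutes of test time in an exploratory feasibility study. It breaches no limit in the protocol and touches no sample-size, power or alpha figure.

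This rests on two assumptions: that the stated total reflects what the authors intended, and, for the figure of 2 minutes per intensity, that each 6-minute block is divided equally. If the first is wrong, the 2-hour listening maximum still holds for the tones and running speech that the Test 2 section describes.

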This is a feasibility study, and the research team is only aware of 1 study by Easwar et al (Ear and Hearing. 2015) comparing detection success rate and detection time for words stimuli during aided and unaided listening conditions is available, with only one word stimulus used in this study. The smallest significant difference in response amplitude between aided and unaided conditions at conversational level was 35 nano-volts (nV) with a within-group standard deviation of 30 nV). Based on these findings, the current study would need to include 29 participants for an ANOVA study to have a power of 80% at an alpha level of 0.01. From analysis of cortical responses to running speech in normal hearing participant, we expect larger variability compared to the results found for words, which led us to decide on a participant number of 40.

Statistical analysis of data

Prior to analysing the results, their normality will be tested. This will guide decision on using parametric or non-parametric statistical tests. Temporal relations between responses will be quantified with correlation analysis. Robustness of responses to noise level will be assessed with an F-ratio test. Statistical significant relationships between EEG channels and the stimulus will be tested using analysis of variance measures. Statistical signal processing methods (including bootstrap methods and confidence limits) will be used in detecting responses.

References

Castro, F.Z., Barajas de Prat, J.J., Zabala, E.L. 2008. Loudness and auditory steady-state responses in normal-hearing subjects. *International Journal of Audiology*, 47:5, 269-275.

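### Does sizing the study on aided-versus-unaided response amplitude, without repeating that comparison in the analysis text, leave research question 1 without an outcome and a test?

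*Combined protocol and SAP*

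**What the plan says.** Research question 1 asks whether brain responses to speech are sensitive to amplification and names no outcome variable. Questions 3 and 4, in the same list, are about detection: which tests detect responses best, and whether realistic speech detects them as robustly as clicks and tones.

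Under Power calculation, the source study is described as "comparing detection success rate and detection time for words stimuli during aided and unaided listening conditions". The figure taken from it is an amplitude: "The smallest significant difference in response amplitude between aided and unaided conditions at conversational level was 35 nano-volts (nV"), with a within-group SD of 30 nV. From this the study "would need to include 29 participants for an ANOVA study to have a power of 80% at an alpha level of 0.01". The number was then raised to 40 because running speech was expected to be more variable.

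Under Data analysis, the response is related to the stimulus by "comparing the stimulus envelope with spectro-temporal features in the (averaged) brain response". Under Statistical analysis of data, a normality check decides between parametric and non-parametric tests. ANOVA appears once: "Statistical significant relationships between EEG channels and the stimulus will be tested using analysis of variance measures". The section ends: "Statistical signal processing methods (including bootstrap methods and confidence limits) will be used in detecting responses". Neither section mentions aided, unaided or amplitude.

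Under Test procedure, "One of the tests will focus on detecting responses to short stimuli (clicks, phonemes and words"). Under Test 1, each participant hears six word conditions, each aided and unaided, and these recordings are assigned to questions 1 and 2.

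**The concern.** The only sized comparison in the protocol does not reappear where the analyses are listed. The one ANOVA listed there has a different object, namely channels and the stimulus. Detection, by contrast, is prominent: it is in the study title, the description of Test 1, the closing analysis sentence and the power paragraph's own account of its source study.

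Two analysts could then take different routes on the same recordings. One would compare mean amplitudes within participants. The other would classify each recording as detected or not and compare paired proportions. The second analysis uses less of the information and can miss an effect that the first one finds. If the choice were made after seeing the data, the answer to question 1 could depend on it, and the sample size was worked out for only one of the two routes.

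**Working it through.** **1. The plan's figure of 29.** Inputs from Power calculation: difference 35 nV, SD 30 nV, alpha 0.01, power 80%. Not stated: number of ANOVA levels, within-person correlation r, whether 30 nV is the SD of one condition or of a difference, and sidedness.

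For a two-condition paired test with 30 nV per condition, the SD of the difference is 30 × √(2(1 − r)) and the standardised effect is 35 divided by that. Noncentral t, two-sided alpha 0.01:

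| r (assumed) | SD of difference (nV) | Effect | n for 80% | Power at 29 | Power at 40 |
|---|---|---|---|---|---|
| 0 | 42.4 | 0.825 | 21 | 94.5% | 99.2% |
| 0.25 | 36.7 | 0.953 | 17 | 98.7% | 99.9% |
| 0.5 | 30.0 | 1.167 | 12 | >99.9% | >99.9% |

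If 30 nV is already the SD of the difference, the last row applies. None of these gives 29. Two other readings come close:
- A six-level repeated-measures ANOVA with r = 0 and the 35 nV gap between two levels only, so f = (35/30) × √(1/12) = 0.337, needs 28.
- Two independent groups, one-sided, normal approximation: 2 × (2.326 + 0.842)² × (30/35)² = 14.7, so 15 per group and 30 in total.

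The inputs therefore do not fix 29, but they do not show it to be too small. For a paired amplitude comparison, 29 and 40 are both more than enough at r of 0 or above. With 40 participants, power stays at 80% until the SD of the difference reaches about 62 nV, which is 62.0/42.4 = 1.46 times the r = 0 value.

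**2. What detection would cost.** Assumptions, none of them in the documents: normal amplitudes with SD 30 nV, aided mean 35 nV higher, and one detection threshold set by the unaided detection rate p. The aided rate is then Φ(Φ⁻¹(p) + 35/30). Exact two-sided McNemar test on one aided/unaided pair, n = 40, range over r = 0 to 0.5:

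| Unaided rate (assumed) | Aided rate | Power, alpha 0.01 | Power, alpha 0.05 |
|---|---|---|---|
| 30% | 74.0% | 88–97% | 97–99.6% |
| 50% | 87.8% | 81–94% | 95–99% |
| 70% | 95.5% | 57–70% | 82–91% |
| 80% | 97.8% | 32–37% | 62–68% |

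The loss is small if half or fewer are detected unaided and large only if most already are. In the last rows a ceiling leaves little gain to find.

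**3. Which outcome the text gives to question 1.**
- *Power calculation* supplies the measure (response amplitude), the contrast (aided versus unaided), the test family (ANOVA) and alpha (0.01). The normality rule in Statistical analysis of data covers the non-parametric alternative.
- *Research questions* gives detection its own place, in questions 3 and 4. Question 1 does not use the word. The title, the Test 1 sentence and the closing analysis sentence can all be read as serving questions 3 and 4.
- *Test 1*: the phrase "showed good detection rate of brain responses" refers to earlier experiments in people with normal hearing. It justifies the choice of stimulus and defines no outcome for this study.

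Read together, amplitude compared within participants is the natural analysis for question 1. No passage states a different one.

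**The case for a change.** The strongest case for a change is that the protocol states a sized comparison at alpha 0.01 and so should say in its analysis section what that comparison is. The analysis section gives ANOVA to another purpose. The same word recordings serve questions 1 and 2, so reading detection as belonging to questions 3 and 4 is an inference, and no primary outcome is defined anywhere. The remedy would take only a few sentences.

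Part of this stands. The analysis text is thin, the inputs behind 29 are incomplete, and 40 rests on judgement about running speech with no SD given. A sentence linking the power paragraph to question 1 would make the document tidier.

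The rest does not carry. An amplitude test that is significant beside a detection test that is not shows a difference in power; it does not put the effect in opposite directions. Detection is also not a single alternative, since the power paragraph mentions detection time, to which a yes/no test does not apply. Reducing six aided/unaided word pairs to one dichotomised pair at alpha 0.01 is a severe choice that the documents do not make. The low power figures depend on assumed unaided detection rates of 70% or more. Naming one word condition as primary, or prescribing a particular model, would be a preference between reasonable analyses and would not correct an error.

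**Conclusion.** No change to the plan follows. It is true that the aided-versus-unaided amplitude comparison is stated under Power calculation and not repeated under Data analysis or Statistical analysis of data. That is an omission of detail. No stated rule gives a wrong result, no two passages prescribe conflicting analyses for question 1, and neither 29 nor 40 is shown to be wrong.

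On the plan's own 35 nV and 30 nV, 40 participants give at least 99.2% power for the paired word comparison, assuming normal amplitudes, two conditions and within-person correlation of 0 or above. Nothing here carries over to running speech, for which the documents give no SD. The 32–97% range for detection at alpha 0.01 rests wholly on assumed detection rates, correlations and a single threshold. In a study that describes itself as exploratory and about feasibility, an analyst would sensibly take the measure and contrast from the power paragraph, use a within-participant test, and report detection beside it for questions 3 and 4.
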